## **B. Significance**

There is a large body of research indicating that schizophrenia is characterized by visual perceptual deficits, with some impairments predating psychosis onset. Indeed, visual distortions and anomalies, which are found in  $\sim 2/3$  of individuals with schizophrenia, are among the strongest predictors of conversion to schizophrenia-spectrum disorders among high-risk youth. It has been shown that in many cases, the impairments on visual processing tasks observed in schizophrenia are not manifestations of a generalized deficit, and are independent of medication effects. Importantly, visual impairments in schizophrenia are significantly related to poorer performance on tasks of visual-related cognitive functions (e.g., visual working memory), impaired social cognitive function, and worse community functioning. Despite this growing literature regarding the significance of visual processing impairments in schizophrenia, there are no accepted visual remediation strategies for schizophrenia, and indeed, this issue has received almost no attention in the literature. Therefore, the goal of the proposed project is to identify a treatment that fills the unmet therapeutic need of alleviating visual perceptual difficulties and related cognitive and behavioral impairments in the disorder. We propose to assess the effects of two complementary forms of visual remediation. One targets the mechanism of *gain control*, and the other targets the mechanism of *integration*. We are using established tests of contrast sensitivity (CS) to operationalize gain control, and established tests of perceptual organization (PO) to operationalize integration. Gain control and integration were identified by the NIMH-sponsored Cognitive Neuroscience Treatment Research to Improve Cognition in Schizophrenia (CNTRICS) initiative as the two core impairments responsible for altered visual processing in schizophrenia. CS and PO have been extensively studied in schizophrenia, their neural mechanisms are relatively wellunderstood (as described later in this section), and their impairments predict higher-level dysfunction. For example, impaired CS has been demonstrated in psychophysical, electrophysiological, and brain imaging studies, and is associated with failures in the later process of PO [Section D.1 Preliminary Data], as well as with poorer facial affect recognition, reading, cognition [ and Section D.1], and community functioning in schizophrenia. PO impairments in schizophrenia have been observed in over 50 laboratory studiesreviewed in 7;8;10, including psychophysical, ERP and fMRI investigations. These visual integration difficulties have also been reported in the clinical literature, an example of which is: "I have to put things together in my head. If I look at my watch I see the watch, the watchstrap, face, hands, and so on, then I have to put them together to get it into one piece"59 (p 229). As with CS, PO deficits are associated with decrements in higher-level function: They are related to impairments in constructing visual representations such as faces from degraded stimuli, forming visual memory representations, and facial emotion decoding. PO impairments are also related to poorer functional outcomes. In addition, abnormal visual PO negatively predicted discharge to the community from a long-term inpatient psychiatric rehabilitation program better than neuropsychological measures of reaction time, attention, memory, and executive functioning, over a 3-year period. Thus, impairments in both CS and PO have predicted poorer functioning. Consistent with this, structural equation modeling (SEM) studies indicate a single pathway from visual dysfunction to functional outcome, with mediating variables that include social cognition. The finding of a single pathway supports a cascade model in which degraded visual representations contribute to difficulties in higher-level processing, and "helps to provide a rationale for early perceptual and cognitive interventions, such as plasticity-based training"65;15 (p1223)

Further motivation for a systematic attempt at visual remediation comes from a growing number of studies demonstrating that plasticity-based visual perceptual learning can occur in both healthy controls and individuals with schizophrenia. We recently published a series of case studies demonstrating improvements in CS in schizophrenia using the CS training program proposed for the current project (, and see section D.1). Moreover, previous studies of visual interventions with non-psychiatric samples, including the CS intervention proposed here, have demonstrated treatment-related gains that generalized beyond the trained visual function, including improved reading skills in controls and people with dyslexia, and improved batting averages in college baseball players, suggesting that improvements in low-level visual processes such as CS can lead to gains in real-world functioning. Regarding PO, we previously published a review on improvements in PO in schizophrenia after repeated task performance (typically over several days), based largely on a number of our earlier contour integration studies. Several studies from other labs have also shown positive effects of perceptual learning-based training programs on visual function in schizophrenia. As noted, however, these investigations used small samples, lacked a control group, used training paradigms with a limited number of sessions, and/or focused on only a single visual task. Finally, a body of work evaluating the effects of a cognitive training program that emphasizes auditory sensory processing has demonstrated significant treatment-related improvements in higher-level auditory and verbal functions in

schizophrenia, such as verbal working memory and verbal learning, suggesting that *training low-level* processes can contribute to improving higher-order cognitive functions dependent on that sensory modality. In short, enough evidence exists to suggest that remediation of visual function is possible, and that it could lead to gains in higher functions that rely on vision. However, despite this promise, and despite visual remediation being a well-developed field in its own right, what is not known is whether, in a well-controlled study with a sufficient sample size and duration of treatment; a) visual processing can be significantly improved in schizophrenia; and b) improvements in visual processing will lead to improvements in higher-order cognition, social cognition, and functional capacity. Therefore, we propose to examine these important questions. We will do so by studying the effects of interventions that have either demonstrated positive effects on visual processing in multiple studies in non-psychiatric populations, or that are based on laboratory measures on which individuals with schizophrenia have demonstrated impairments, but also perceptual learning-based improvements, in multiple prior studies. Based on: a) data showing strong evidence for visual impairments in schizophrenia that are thought to reflect core components of the disorder; b) relationships between these impairments and cognition, social cognition, functioning, illness course, and treatment outcome in cross-sectional, SEM, and longitudinal studies; and c) knowledge that visual processing can be improved in psychiatrically-healthy subjects and (based on preliminary data) in people with schizophrenia, this intervention, if effective, has the potential to significantly reduce the burden of serious mental illness by improving perceptual and cognitive functioning in schizophrenia.

As noted, the first level of remediation that we will evaluate targets gain control, in the form of CS. To remediate CS impairments in schizophrenia, we will use the ULTIMEYES (UE) computerized intervention, which targets CS across a wide range of spatial frequencies. **UE is ready for early-phase testing** in participants with schizophrenia, as it has been successfully developed as a computer application by [name] (a co-investigator on this grant proposal).

To assess target engagement for CS, we will use two complementary paradigms, one psychophysical and the other electrophysiological, both of which were recommended by the CNTRICS initiative to assess the construct of gain control in vision. Psychophysical CS assesses the lowest level of contrast needed to detect stimuli presented at different spatial frequencies (SFs) (i.e., fine to broad lines corresponding to high to low SF, respectively). Studies of psychophysical CS show that people with schizophrenia need greater contrast (i.e., show lower CS) than controls to detect contrast across the ronange of SFs, although deficits in processing low SF (LSF) stimuli have been more pronounced in most studies of schizophrenia. In addition, deficits in LSF processing are related to object recognition as well as to face and facial emotion processing deficits in schizophrenia. Therefore, we focus primarily on CS for LSF stimuli. Because features within LSF stimuli are relatively large, there is less of an effect of acuity on those responses as opposed to fine-grained HSF stimuli that rely heavily on acuity. This helps to address the potential confound of impaired acuity in people with schizophrenia on task performance. However, supporting the hypothesis that acuity was not driving past CS results are findings that the relationships between impaired CS and poorer facial emotion recognition, reading, visual learning, and PO in people with schizophrenia (13;27;29;81 and Preliminary Data) are strongest for LSF stimuli. Electrophysiological CS involves recording the steadystate visual evoked potential (ssVEP) in response to stimuli varying in contrast. The ssVEP measure provides rapid, objective assessment of visual cortical responses to a range of contrast levels without requiring *behavioral responses from participants.* Studies of ssVEP in schizophrenia consistently show impairments, and these are most pronounced at low contrast levels. Weaker ssVEP responses to contrast changes in schizophrenia are significantly correlated with behaviorally-assessed CS, facial emotion recognition, Global Assessment of Functioning (GAF) scores, and Problem Solving Factor scores on the Independent Living Scale.

The neural mechanisms involved in CS are relatively well understood. As noted above, CS has been viewed as a form of gain control. Gain control involves both amplification and suppression of signals to keep neural activity at or near optimal levels; this homeostatic function thereby serves to reduce the risk of sensory deprivation-induced hallucinations with insufficient cortical activation, and stimulus overload with excess activation. Weaker signals, such as those involving low contrast and/or LSFs are amplified, and stronger signals are attenuated, with the full contrast-response function therefore following a classic sigmoidal curve. At the neural level, both amplification and attenuation are thought to arise from divisive normalization, in which target signal strength is modulated as a function of total activation in the cortical region. Evidence that observer CS in a psychophysical task corresponds with level of neural activation, and that it is modulated by gain control, comes from several sources. One is that, using single-unit microelectrode recording in cat V1, the inverse U-shaped psychophysical CS function (CSF) was highly correlated with the neuronal

CSF. Another is that the fMRI BOLD response in V1 in humans covaries with contrast enhancement and SF, with the relationship being especially tightly coupled for LSF stimuli. In short, gain control keeps responses within an adaptively limited signaling range, and both of the CS assessment formats we propose to use generate data that can be interpreted clearly within cognitive neuroscience models of gain control in schizophrenia and healthy populations.

The second level of remediation in the R61 targets integration, in the form of PO. We are focusing specifically on the visual PO function of contour integration. We have developed a program for contour integration training (CIT), via modification of a contour integration task developed for use in schizophrenia by [name] and colleagues, and used previously in multiple behavioral, ERP, and fMRI studies. Our hypothesis regarding the ability of CIT to drive gains in PO is based on prior demonstrations of perceptual learning in controls and participants with schizophrenia (albeit at a slower rate in the latter group) with similar versions of this task. For example, healthy controls showed improved detection of a collinear path over 12 days of training, improved performance on a closed contour integration task across test sessions that spanned 2 consecutive days, and gains in identifying interpolated shapes over 4 days. In addition, in monkeys, behavioral performance and V1 activity increased consistently over 10 days of contour integration training. People with schizophrenia showed improved contour integration performance following 2-4 days of exposure to the task in the study cited above in which controls reached asymptotic performance after 2 days, and improved pattern recognition across a single session of training involving 600 trials. In addition, there are numerous studies that provide validity, reliability, and short-term perceptual learning data for the contour integration paradigm. A further advantage of this task is that the neural mechanisms underlying performance have been demonstrated in monkeys and healthy humans, and neural correlates of impairment (e.g., in V2, V3, V4, LOC, and frontal-parietal regions) have been identified in participants with schizophrenia. Therefore, demonstration of improved performance after remediation would lead naturally to EEG and fMRI studies of training-related activation changes in specific regions of interest and brain networks.

To assess target engagement for the PO intervention (CIT), we will use two tasks. The first is the original contour integration test recommended by the CNTRICS initiative for use in treatment studies of schizophrenia, namely the Jittered Orientation Visual Integration (JOVI) task. The JOVI involves identifying the direction of an egg-shaped contour made up of individual Gabor elements with gaps between them so that the participant has to perceptually integrate the Gabors to perceive the egg (see Fig. 3). The task has been optimized for use in clinical trials (see D.6.b). Although there are differences between the PO training task (CIT) and the JOVI in terms of the specific stimuli (i.e., circular vs. oval shapes, respectively) and response requirements (identifying the location of the target circle vs. indicating whether the centrallypresented egg-shaped contour is pointing left or right), which should preclude confounds based on low-level perceptual learning (e.g., learning that is specific to one area of visual space, or to a single shape), we will also include a second outcome measure, one that does not share method variance with the training task. The second PO task uses the Ebbinghaus illusion, in which a center circle appears smaller if it is surrounded by (i.e., grouped with) larger circles and appears larger if it is surrounded by smaller circles (see Fig. 5). The task requires subjects to choose which display (on the left or right of the screen) contains the array with the larger central circle. By manipulating the difference between the actual sizes of the central circles, and whether the size of the surrounding circles causes the inner target circle to appear smaller or larger than its actual size, a psychophysically precise measure of illusion strength is obtained. [name] has used this task extensively, and one of its appealing aspects is that, due to their reduced grouping of the central target and the surrounding circles, people with schizophrenia perform more accurately (in all studies cited above) than controls on trials in which surrounding context is normally misleading (e.g., when the larger of the two inner circles is made to appear smaller by surrounding it with large circles). Evidence that both the JOVI and Ebbinghaus tasks involve PO comes from a significant *inverse* correlation between scores such that a lower score on the JOVI is associated with higher scores in the misleading condition on the Ebbinghaus task.

As with CS, the neural mechanisms of PO, and of contour integration in particular, are relatively well understood. One involves long-range horizontal connections between orientation-tuned spatial frequency detectors in V1 (especially important for integrating closely spaced elements). A second involves reentrant feedback from V4 and higher visual areas to V1 and V2 (most important for grouping more distantly spaced elements) to amplify processing of elements belonging to a single contour, surface, or shape. Importantly, contour integration cannot be implemented purely by local spatial frequency detectors, or by orientation-tuned neurons with large receptive fields; rather, integration of activity across sets of neurons is required. Single-cell studies in V1 suggest excitatory (facilitating) effects when contour elements are collinear, but not orthogonal, with a central target. fMRI data in humans and monkeys indicate that V1, V2, V3,

V4, and the LOC are more activated when processing Gabor-defined contours, in contrast to randomlyoriented Gabors. In addition, activation of the prefrontal cortex and posterior parietal lobe are associated with successful contour integration, presumably as a source of feedback to occipital regions. However, it has been shown that impaired contour integration in schizophrenia is not due to inattention or random responding during task performance. Both lateral excitation and top-down feedback, as implemented in contour integration, and in PO in general, are thought to involve synchronization of beta- and gamma-band oscillatory activity between neurons signaling contour elements (which are typically collinear or co-circular), and also between these temporary networks and top-down attention signals. Relatedly, impaired PO in schizophrenia is associated with reduced synchrony within these bands. This impairment is thought to reflect both NMDA receptor hypofunction and reduced GABAergic signalingreviewed in 86;122;123.

Clear and refutable hypotheses of the R61 are: H1a) UE or UE&CIT will lead to significantly greater gains in CS than will ACCT and/or H1b) CIT or UE&CIT will produce significantly greater improvements in PO compared to ACCT. The **Go Signal** for continuing to the R33 will be a differential improvement, with an effect size of at least d=0.4, favoring UE or UE&CIT compared to ACCT on the psychophysical and/or electrophysiological CS task, *and/or* CIT or UE&CIT compared to ACCT on the JOVI and/or Ebbinghaus task. If a "go" signal is obtained, results of the R61 will be used to identify the most effective and efficient treatment (UE, CIT, or UE&CIT), and duration/dose, for use in the R33.

**Clear and refutable hypotheses of the R33 are:** H1) The optimal treatment identified in the R61 (e.g., UE&CIT) will be more effective than the control treatment (ACCT) in improving CS or PO in a new and larger sample; and H2) Improvements in target function will be related to changes on visual cognitive (i.e., visual learning and memory, reading), social cognitive (i.e., facial emotion recognition) and functional capacity measures. If the hypotheses in the R33 are confirmed, the results will inform the design of a later RCT to assess the efficacy of a visual remediation treatment for schizophrenia on a wider range of outcome variables. Instructions for the R33 state that it "should not be powered as strong tests of clinical efficacy but rather should test the link between... target engagement and functional outcome." Therefore, while we expect the correlations for R33 Aim 2 to be statistically significant, we do not hypothesize what the effect sizes will be. However, we would power a subsequent study based on the observed effect sizes in the R33.

*This project will advance knowledge of intervention and disease mechanisms,* whether the trial results are positive or negative. In the R61, we will learn whether targeting either or both levels of visual function improves the perceptual targets. The assessment of whether changes in the visual targets drive changes in other functions in the R33 will provide information about disease mechanisms by clarifying the links between visual perception and cognitive and social cognitive function. *We also wish to note that although there are multiple ways that a 'go' signal in the R61 can be achieved, each of these possibilities would represent a novel finding in its own right and motivate further studies of visual remediation in schizophrenia. More importantly, however, the R33 will serve, in part, as a replication and extension study of the R61: Observing that the optimal R61 intervention is effective in a second study, with a new and larger patient sample, and a similar degree of target engagement, would provide confidence that any R61 findings are not spurious.* 

At a more basic level, as noted above, we are studying the effects of targeting basic forms of gain control and integrative processes on higher-level perceptual and cognitive processes. We are including two intervention components (UE and CIT) in order to explicitly target both CS and PO because there is evidence that both aspects of visual function are impaired in schizophrenia AND that impairments in both are related to poorer functioning in multiple domains. Because this is the first controlled study of perceptual remediation of these functions in schizophrenia, we wish to remain agnostic regarding whether the combined treatment (UE&CIT) will be more effective than either UE or CIT alone, although we anticipate that the combination may have additive or synergistic effects on one or both levels of vision. By assessing improvements related to the single treatment (UE or CIT) AND to the combined intervention at each level of vision, we will be able – at the end of the project – to provide a strong initial statement regarding the important question of differential and combined intervention effects. Future clinical trials will determine whether there are subgroups of individuals with schizophrenia (e.g., those who are more impaired on CS or PO at baseline) who are especially likely to benefit from these interventions. This is not a specific aim for this initial clinical trial because even people without visual impairment can improve their visual functioning; however, our data will allow us to assess the degree to which improvement is a function of baseline CS and PO.

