# D.3 R61 Phase

Aims: (i) To evaluate the effects of UE and CIT on the CS and PO targets, respectively; (ii) to determine if the criterion for continuing to the R33 phase is met; and (iii) if the criterion is met, to determine the most effective intervention condition and optimal duration of treatment, to inform the R33 study design.

Study design: 80 subjects will be enrolled in this study: 20 per arm. 40 will be recruited at each site (Rutgers and NKI). The intervention will continue for 40 sessions, with targets assessed before training, after every 10 sessions, and at 6 months post-training for a total of 6 visual assessments. With 3 sessions per week, the intervention will take between 13-14 weeks. Each site will enroll ~ 2 participants/month, beginning after the first half of Y1, which is similar to what Keefe et al. estimated as a "reasonable rate of recruitment for a largescale efficacy trial" of cognitive remediation. Because, at the 6-month follow-up, nearly all patients are expected to still be in the partial hospital program, or an outpatient program (at Rutgers), or on inpatient units at the Rockland Psychiatric Center (RPC) or NKI, we expect attrition to be minimal. However, several methods, including monthly phone calls (see Recruitment and Study Timeline), will be used to maximize retention. For the R61 and R33, training sessions will be run in small groups by front-line staff who have already received training in these interventions, or whom we will train, with no more than a 3:1 participant:staff ratio. Randomization: Subjects will be randomly assigned, within site, to one of the 4 conditions (UE&ACCT, CIT&ACCT, UE&CIT and ACCT&ACCT) in a ratio of 1:1:1:1. The treatment assignment will be made after a subject has met all entry criteria and completed baseline testing, to avoid bias.

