Milestones (Go/No-Go Criterion): We will proceed to the R33 phase if: 1) the UE-related effect size (i.e., the effect size of the difference between the UE&ACCT (or UE&CIT) and ACCT&ACCT groups in the degree of change in CS) is greater than or equal to Cohen's d=0.4 for **either** the psychophysical **or** ssVEP CS task: and/or 2) the CIT-related effect size (i.e., the effect size of the difference between CIT&ACCT (or UE&CIT) and ACCT&ACCT groups in the change on **either** of the PO tasks) is greater than or equal to d=0.4. Pre-post change scores for CS and PO target assessments will be calculated for each individual and used to determine effect sizes between groups. We will not control for baseline values consistent with recommendations to use "straight" change scores when examining cognitive change across two time points.

Rationale for our effect size choice: The effect size criterion we have chosen for the R61 "go" signal (d=0.4)

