is similar to that observed in many studies of cognitive remediation, and of other treatments for this population, such as skills training and family psycho-education. However, less is known about effect sizes of perceptual remediation, and most of the evidence on this in schizophrenia comes from studies of auditory remediation using the Posit Science auditory training module, which includes training on both low-level auditory targets and higher-level auditory-verbal cognition (e.g., verbal working memory and learning). Results from one study indicated an improvement in the target of auditory-processing speed that was of large effect (d=0.875). The authors also observed a medium-large effect on global cognition (d=0.73). Results from other studies of this auditory training module in schizophrenia have indicated large treatment effects (d=0.86) for both verbal learning and global cognition, and a medium effect (d=~0.65) on the auditory target of P50 gating. While these effect sizes are larger than our chosen criterion (d=.4), it is also important to note that some studies of Posit Science modules have not demonstrated significant improvement on non-trained tasks. Moreover, across studies, the largest effects have tended to come from studies where daily training (5 days a week) was used, and subjects were paid for completing training sessions, and these are two conditions that can rarely be met in real world psychiatric clinics. These considerations have informed our choice of the 'go signal' criterion (i.e., d=.4), because there are as of yet very few published studies of visual remediation in schizophrenia. One small (N=9) uncontrolled study of visual backward masking training found an effect size of d=.43 for improvement in the MATRICS domain of Visual Learning. Within our group, [name] observed an improvement in contour integration performance among participants with schizophrenia after 4 consecutive days of practice on a contour integration task (phi=0.63, which corresponds to a large effect). Even larger effect sizes were seen for changes in CS (d=0.96), and PO (d=0.85) in our small pilot sample of patients with schizophrenia (Section D1), but given the small sample size and lack of a control group in that study it can be assumed that the real effect size is lower. Thus, findings from these initial evaluations of visual remediation support our use of d=0.4 as a conservative level of change on the outcome measures and as a "go" signal for target engagement. However, we acknowledge that it is not yet clear from the literature how an effect of this size relates to meaningful improvements in visual and higher-order cognitive processing, and/or functional capacity. The proposed R33 will allow us to address this guestion in a preliminary manner. If results from this trial are positive, we will seek funding for a larger trial to evaluate the impact of this treatment on functional outcomes, and to identify mediators/moderators of treatment response. If the Go criterion is met for any of the treatment conditions, we will perform a thorough investigation of the effects of UE, CIT, and UE&CIT on the CS and PO target scores to determine which remediation strategy to use for the R33. Analyses will also include (i) assessment of the trajectory of performance on the target measures over the course of treatment; (ii) determinations of whether the improvements plateau prior to the 40th session or whether they continue throughout the training period; and (iii) evaluations of whether any combined effects of UE and CIT are additive or multiplicative. These goals will be accomplished by first graphically examining the trajectories of target change to assess whether they are linear, monotonic non-linear, guadratic, or any other shape. After that, appropriate models for longitudinal data analysis will be applied to estimate improvement rate and time to asymptote. We will account for CPZ-equivalent dose of antipsychotic medications in all models, using CPZ dose as a time-varying covariate if necessary, and will also account for type of antipsychotic medication and anticholinergic load. Those models will also be used to examine whether baseline characteristics moderate the effect of UE and/or CIT on the targets. These analyses will allow us to ascertain: 1) whether UE alone, by targeting CS function, has a cascading effect on PO; 2) whether CIT improves CS while targeting PO function; and 3) whether UE&CIT has a stronger effect than either intervention alone for any outcome. Based on these results, the optimal intervention will be determined based on it having a significantly larger effect size for at least one target. If all 3 treatment conditions are effective to an equivalent degree, the criterion will be reaching asymptotic level of improvement earliest.

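### The R61 go rule passes if any one of eight point estimates reaches d=0.4; with no true effect that happens in about 43-55% of trials under stated assumptions, and the plan gives no false-go rate

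*Combined protocol and SAP*

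**What the plan says.** Section D.3 (Study design) sets the size: "80 subjects will be enrolled in this study: 20 per arm". Randomization within site is to "UE&ACCT, CIT&ACCT, UE&CIT and ACCT&ACCT) in a ratio of 1:1:1:1", so a single arm of 20 serves as control for every comparison.

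The go signal is defined in B. Significance and again in D.3 (Milestones). For contrast sensitivity (CS) it is a differential improvement "favoring UE or UE&CIT compared to ACCT on the psychophysical and/or electrophysiological CS task". For PO it is "CIT or UE&CIT compared to ACCT on the JOVI and/or Ebbinghaus task". The D.3 wording is that the effect size "is greater than or equal to Cohen's d=0.4 for" either task of a target. On the scale, D.3 says: "Pre-post change scores for CS and PO target assessments will be calculated for each individual and used to determine effect sizes between groups". Baseline values are not adjusted for.

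Two sentences describe what a go would mean. B. Significance acknowledges that there are several routes to a go and says "each of these possibilities would represent a novel finding in its own right". D.3 (Rationale for our effect size choice) says the early findings "support our use of d=0.4 as a conservative level of change on the outcome measures", and in the same sentence presents 0.4 as the go signal for target engagement. Neither section gives the probability of a go when training does nothing. The Bonferroni statement is in the R33 data analysis in D.4 and does not cover this gate.

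**The concern.** The threshold applies to an estimate, with no bound on its error, and the estimate may come from any of eight comparisons. With 20 per arm the standard error of one d is about 0.32, so 0.4 is only about 1.3 standard errors from zero. Taking the best of eight makes a value that large common under pure noise.

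The go decision opens a trial of 100 further participants, and the R61 results guide the choice of R33 treatment and duration. If any single route is read as a demonstration that a target was engaged, the R61 will claim more than its rule can show. The decision to continue would also be taken without knowing how often the rule passes ineffective training.

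**Working it through.** **Inputs.** From the documents: 20 per arm, four arms, one shared control, threshold 0.4 on between-group d of individual change scores (D.3); two arms by two tasks for each of two targets (B. Significance, D.3), so 2 x 2 x 2 = 8 comparisons; and r=.41 between the VEP and psychophysical CS indices (D.6.b). That r is for index levels, not change scores. All other correlations are assumptions.

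**The plan's own precision figure.** The sample-size paragraph in D.3 gives a 95% CI of .02 to .91 at d=0.4. With n per group, SE(d) = sqrt(2/n + d²/(4n)).
- n=20: sqrt(0.100 + 0.002) = 0.319, so 0.4 ± 1.96 x 0.319 = **-0.23 to 1.03**. The noncentral-t interval is the same.
- Other layouts do not reproduce the stated interval either: 40 v 20 gives -0.14 to 0.94, 40 v 40 gives -0.04 to 0.84, and one sample of 20 gives -0.06 to 0.86.
- For the lower limit to exclude zero, n must be at least 2.04 x (1.96/0.4)² = 49 per group.

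The stated interval is said to draw on pilot data that are not shown. It does not follow from 20 per group.

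**One comparison, no effect.** Under the null, SE = sqrt(2/20) = 0.316, and 0.4/0.316 = 1.265. P(Z ≥ 1.265) = 0.103; P(t38 ≥ 1.265) = 0.107.

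**Any of eight, no effect.** Eight independent comparisons would give 1 - (1 - 0.107)^8 ≈ 0.59, an upper reference. The real comparisons share a control arm and correlated tasks, so they were simulated: four arms of 20, normal change scores, pooled-SD d, go if any of the eight is at least 0.4, and at least 20,000 trials per setting.

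| Correlation within / between targets | P(go), no effect |
|---|---|
| 0 / 0 | 0.54-0.55 |
| 0.2 / 0.1 | 0.51-0.52 |
| 0.41 / 0 | 0.50 |
| 0.41 / 0.2 | 0.48 |
| 0.41 / 0.41 | 0.45-0.46 |
| 0.6 / 0.4 | 0.43-0.44 |

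**Sensitivity.**
- Stronger correlation: 0.37 at 0.8/0.7; 0.23 if all four measures were perfectly correlated.
- Pooling the two arms that contain a component (40 v 20, four comparisons): about 0.20-0.27.
- Standardising by baseline SD with an assumed pre-post correlation of .7: SD of change is sqrt(2 x 0.3) = 0.775 of baseline SD, which gives about 0.25-0.33.
- Taking the SE implied by the plan's stated interval, (0.91 - 0.02)/(2 x 1.96) = 0.227: about 0.21-0.27.

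**A composite as an alternative gate.** Each target uses the mean of its two standardised change scores, giving four comparisons. Ranges are over the settings 0/0 to 0.6/0.4; the true effects are on CS in both arms that contain UE.

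| Truth | P(go), current rule | P(go), composite |
|---|---|---|
| No effect | 0.43-0.55 | 0.30-0.34 |
| d=0.4 on both CS tasks | 0.83-0.93 | 0.75-0.87 |
| d=0.4 on one CS task | 0.73-0.82 | 0.50-0.61 |

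**The case against.** The strongest reply is that this is a deliberately permissive first gate with a safeguard behind it. B. Significance discloses the several routes. It then relies on the R33, a randomised comparison in a new and larger sample, to show that R61 findings are not spurious. That design is defensible, and this part of the reply stands. It does not supply the missing error rate, and it does not turn the go itself into a finding.

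Four stronger readings are tempting, and the documents do not support them.
- *That calling 0.4 conservative is a false claim about error.* In D.3 the word compares 0.4 with earlier, mostly larger effects (0.43, phi=0.63, 0.85, 0.96). It says nothing about how often noise reaches 0.4.
- *That the go is the R61's formal test of target engagement.* Aim (ii) is to determine whether the continuation criterion is met. Evaluating effects on the targets is aim (i), and H1a and H1b call for significant differences. The only support for the stronger reading is the loose phrase in D.3 linking the go to target engagement.
- *That a false go by itself fixes the R33 on noise.* D.3 adds a second step: the chosen treatment must show a significantly larger effect on at least one target, with a time-to-asymptote rule if all three are equivalent. D.4 keeps all four visual tests whichever treatment is chosen.
- *That the gate must be rebuilt on composites.* A composite still passes about three null trials in ten and loses over 20 points of P(go) when only one task improves. It would also blur the reason for the Ebbinghaus task, which was added because it shares no method variance with the training.

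The 43-55% is also conditional, as the sensitivity checks show. The pooled-arm and baseline-SD readings fit the text less well: the rule offers the arms as alternatives and bases effect sizes on change scores. Even so, those readings give about twice the single-comparison rate or more.

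**Conclusion.** The concern holds as a matter of what a go can be taken to show. With no effect of any training on any of the four measures, 20 analysed per arm and d standardised by the SD of change, the rule gives a go in about 43-55% of trials over the assumed correlations. The figure is about 48% at 0.41/0.2, the setting that extends the one documented correlation to both targets. It is 20-33% under the pooled-arm or baseline-SD readings. Because the interval at d=0.4 with 20 per group runs from about -0.23 to 1.03, reaching the threshold on one route is not in itself evidence of target engagement or a finding in its own right.

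The gate is disclosed and a replication follows it, so the weakness is an unquantified criterion described too favourably. It does not invalidate the design. Severity: should-fix.

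**What to change.** 1. In D.3 (Milestones), state the false-go probability next to the criterion, with its assumptions: eight comparisons, shared control, 20 per arm, SD of change as the standardiser, and the correlations used.
2. In B. Significance and D.3 (Rationale), describe a go as a permissive screening signal. Replace the sentence that treats each route as a finding. Say that R61 target engagement is judged by the H1a/H1b tests and by replication in the R33.
3. In D.3 (Rationale), make clear that the word conservative refers only to size relative to earlier effects.

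These are wording changes. They need no new data and leave the chance of a go unchanged. The cost is a less favourable description of the go.

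Optional, for the sponsor to weigh: one pre-specified composite per target, with the trade-off tabulated above. If it is used, the directions must be aligned, since a lower ssVEP contrast threshold is better while higher CS is better. The plan would also need to say how the PO composite is formed for participants excluded by the JOVI catch-trial rule in D.6.b.
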